## 6 Statistical methods for Pharmacokinetic (PK) parameters

All subjects with at least one period of evaluable pharmacokinetic (PK) parameter data will be included in the pharmacokinetic data analysis.

### 6.1.1 Variables

In Part 1, the pharmacokinetic parameters include (but are not limited to) AUC, Cmax, Tmax for LJN452.

Plasma concentrations will be expressed in ng/mL. All concentrations below the limit of quantification or missing data will be labeled as such in the concentration data listings. Concentrations below the Limit of Quantification will be treated as zero in summary statistics for concentration data only. They will not be considered for calculation of PK parameters (with the exception of the pre-dose samples).

### 6.1.2 Descriptive analyses

Descriptive statistics of pharmacokinetic concentration and parameters will include mean (arithmetic and geometric), SD, CV (arithmetic and geometric), median, minimum and maximum. An exception to this is Tmax where median, minimum and maximum will be presented. Concentrations below LLOQ will be treated as zero in summary statistics and for PK parameter calculations. A geometric mean will not be reported if the dataset includes zero values. Pharmacokinetic parameters will be listed by treatment and subject.

At Day 1 and Day 28, AUC and Cmax will be summarized for each cohort along with 90% two-sided confidence intervals computed on the log-scale and back-transformed. All subjects with available PK parameters and no protocol deviation excluding them from the PK analysis set will be part of this computation.

LJN452 plasma concentration data will be listed by treatment, subject, and visit/sampling time point. Descriptive summary statistics will be provided by treatment and visit/sampling time point, including the frequency (n, %) of concentrations below the LLOQ and reported as zero. Additionally summary statistics may also be provided for the LJN452 plasma concentration data with a breakdown by UDCA stratum as appropriate.

### **6.1.3 Statistical model, assumptions and hypotheses**

If 3 or more cohorts are included in Part 1 of the study, then dose-proportionality will be explored by fitting a power model to log(AUCtau) and log(Cmax). The model will specify a linear regression in log AUC (resp. log Cmax) regressed onto log dose level. This analysis will be done at Day 28 only.

Dose proportionality will be assessed on pharmacokinetic parameters AUCtau and Cmax on Day 28.

The pharmacokinetic parameters will be used to explore the relationship between dose and pharmacokinetic parameters using the power model on the log scale:

$$\ln(PK_{ij}) = \mu + \beta \ln(Dose_j)$$

with  $\beta$  denoting the slope and Dosej denoting the total dose.

An estimator for the slope including the 90% confidence interval will be obtained based upon the log-transformed observations. This estimator and confidence interval will then be “back-transformed” to the original scale.

For exploratory information, PK dose proportionality will be considered across the whole dose range if the 90% confidence interval ( $\beta_L, \beta_U$ ) for the slope  $\beta_j$  is completely contained within a pre-specified critical region ( $b_L, b_U$ ), where the two limits  $b_L, b_U$  are derived as follows:

$$b_L = 1 + \ln(\theta_L)/\ln(r) \text{ and } b_U = 1 + \ln(\theta_U)/\ln(r)$$

with  $r$ =ratio of doses (highest dose/lowest dose),  $\theta_L=0.8$ ,  $\theta_U=1.25$  being the standard bioequivalence limits.

Graphical representation of dose proportionality will be explored.

### **6.1.4 Model checking procedures**

The quality of the fit of the power model to assess dose-proportionality will be assessed by comparing the linear sub-model against a saturated model with a different mean level at each concentration. In case of evidence of lack-of-fit, alternative models will be explored.

### **6.1.5 Graphical presentation of results**

Arithmetic mean (SD) plasma concentration data will be plotted across time, with separate line types for each population.

Overlaying individual plasma concentration-time profiles will be generated.

### **6.1.6 Pharmacokinetic / pharmacodynamic interactions**

The relationship between PK (dose, concentration or PK parameter such as Cmax and AUC on Day 28) and key PD parameters (absolute and change from baseline to Day 28) including the primary endpoint GGT, the secondary efficacy/PD variables (PBC-40 total score, PBC-40 itch domain subscore, and the VAS scale PRO), [REDACTED]

[REDACTED] will be explored by graphic exhibition.

## **7 Statistical methods for Pharmacodynamic (PD) parameters**

Analysis will be done for Part 1 and Part 2 separately unless specifically mentioned.

### **7.1 Primary objective**

The primary efficacy objective is to evaluate the treatment effect of LJN452 over placebo in terms of reduction in cholestasis. The primary efficacy endpoint is the fold change in serum gamma-glutamyl transferase (GGT) from baseline to Day 28 and Day 85 for Part 1 and Part 2, respectively.

#### **7.1.1 Variables**

The primary efficacy endpoint is the fold change in serum GGT from baseline.

The serum GGT values at all time points will be logarithmically transformed prior to analysis. The rationale for the log transformation is to achieve more approximate normality and to be able to estimate a treatment effect on a ratio scale.  $Y = \log(GGT + 0.0001)$  will be considered only if there are many observations with GGT result as zero.

The change from baseline will be calculated as the difference between each of the log-transformed post-dose serum GGT values and the log-transformed baseline serum GGT value. This change from baseline will then be “back-transformed” to give a fold increase from baseline.

Baseline will be latest available pre-dose measurement.

#### **7.1.2 Descriptive analyses**

Unless stated otherwise, summary statistics for PD variables will include sample size (n), mean (arithmetic and geometric), SD, CV (arithmetic and geometric), median, minimum and maximum. A geometric mean will not be reported if the dataset includes zero values.

Summary statistics will be reported by treatment at each applicable time point for the original data and also the change from baseline or fold increases from baseline or percent change from baseline, as appropriate.

#### **7.1.3 Statistical model, assumptions and hypotheses**

Log-transformed changes from baseline for serum GGT will be analyzed by repeated measures analysis of covariance (ANCOVA) for each Part 1 and Part 2 separately. The model will include

treatment as a fixed effect, time as a repeated effect, the treatment by time interaction, the time by log-transformed baseline interaction and log-transformed baseline as a continuous covariate. The UDCA and pruritus stratification factor will also be included as a fixed effect in the ANCOVA model for the Part 2 analysis. A saturated covariance structure will be used for observations within the same subject. The model will be fitted using SAS Proc Mixed and the restricted maximum likelihood scoring method (reml). Two-sided 90% confidence intervals for the difference between each LJN452 dose and placebo will be evaluated for each visit. This will then be “back-transformed” to the original scale to give a fold change from baseline. Dose response may be assessed using appropriate contrasts. The analysis at the Day 28 (Visit 7) and day 85 (Visit 7) will constitute the primary analysis for Part 1 and Part 2, respectively.

The analysis will be done for each study cohort using pooled placebo data within Parts 1 and 2, respectively. No adjustment for multiplicity will be done.

Additionally an exploratory analysis on the combined data from Part 1 and Part 2 may be performed using a similar approach and the correlation between measurements taken in Part 1 and Part 2 from the same subject will be accounted for as appropriate.

Similar analysis as mentioned above can be performed for key LFT parameters.

In Part 2, there is the option of reducing the dose level for the individual subject. If for any subject the dose is reduced during the study, any data after the dose reduction will be set to missing. A repeated measures ANCOVA treating all measurements obtained post dose reduction as missing will be performed as well for Part 2 only.

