If the additional laboratory evaluation confirms the increase of ALT and/or AST values, the study treatment will be reduced to the next dose level in a blinded manner ([Table 6-1](#)). The procedure for dose reduction is outlined in the Site Operations Manual.

If the additional laboratory evaluation does not confirm the significant increase of ALT values, the patient will continue with the assigned/original dose level.

If the additional laboratory evaluation shows a higher elevation of ALT and/or AST (e.g. $> 8 \times$ ULN) as compared to the original elevation (e.g. $> 5 \times$ ULN but $\leq 8 \times$ ULN), the guidance for this higher elevation (e.g. $> 8 \times$ ULN) should be followed.

Table 6-1 Part 2 Permitted dose reductions

Original treatment (daily dose)	Reduced treatment (daily dose)
Dose Level 1	Placebo
Dose Level 2	Dose Level 1
Placebo	Placebo

Repeat/second dose reductions are not permitted. Returning to the original treatment is not permitted.

Patients with a persistent or a second cycle of elevated ALT or AST while on the reduced dose will be instructed to return to the clinic for repeat tests as outlined in [Table 15-1](#). If the repeat tests confirm the elevated ALT or AST values, the patient will discontinue study treatment. If the repeat tests do not confirm elevation, the patient will continue with the reduced dose.

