11.4.2 Statistical model, hypothesis, and method of analysis

Changes from baseline for log transformed serum GGT will be analyzed by repeated measures analysis of covariance (ANCOVA) with a fixed effect for the treatment, visit, treatment*visit interaction, log-transformed baseline as well as log(baseline)*visit interaction. The UDCA and pruritus stratification factor will also be included as a fixed effect in the ANCOVA model for Part 2 analysis. A saturated covariance structure will be used for observations within the same subject. The model will be fitted using SAS Proc Mixed and the restricted maximum likelihood scoring method (reml). Two-sided 90% confidence intervals for the difference between each LJN452 dose and placebo will be evaluated for each visit. This will then be “back-transformed” to the original scale to give a fold change from baseline. Dose response may be assessed using appropriate contrasts. The analysis at the 28 day visit and 85 day visit will constitute the primary analysis for Part 1 and Part 2, respectively. The analysis will be done for each study part using pooled placebo data within parts 1 and 2, respectively. No adjustment for multiplicity will be done.

Similar analysis as mentioned above can be performed for key LFT parameters.

Additionally a repeated measures ANCOVA treating all post dose reduction measurements as missing will be performed as well.

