## 1 Introduction to RAP documentation

### 1.1 Scope

The RAP documents contain detailed information to aid the production of Statistics & Programming input into the Clinical Study Report (CSR) for trial “**CLJN452X2201**”.

**Module 3 (M3) provides the description of the statistical methodology** used to analyze the data, **TFL shells** details the presentation of the data, including shells of summary tables, figures and listings, and **Module 8 (M8)** contains programming specifications e.g. for derived variables and derived datasets, to support the creation of CSR outputs.

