### 1.2 Changes to RAP documentation (M3)

Refer to corresponding guidances and NIBR RAP Addendum template for detailed information on the requirements of documenting changes to RAP documentation.

**For the statistical methodology (M3),** any major changes to the statistical methodology should be reflected in the RAP M3 documentation via version control (M3 amendment) (new document version to be approved by the trial team as the original module).

Such major changes could include (but are not limited to):

- change in statistical methodology
- substantial change in (derivation of) main endpoint
- substantial change in study design (e.g. protocol amendment introducing new multiple-dose cohorts in a so far single-dose trial)

Such changes may also require a protocol amendment to ensure consistency. In addition they need to be mentioned (high-level) in the CSR (section for changes to planned analysis).

Minor changes to the RAP M3 documentation can be captured e.g. by a study note to file / note in RAP Addendum or within the CSR itself.

Corrections of typographical errors or modification of spelling (from English to American, for example) do not need to be incorporated into the RAP M3 documentation.

This RAP M3 Amendment 1 is to reflect the following changes:

- The addition of a deviation code leading to exclusion from the PD analysis set in Table 5-1.
- The addition of the time by log-transformed baseline term in the repeated measures analysis model in Section 7.1.3.
- The changes to the study design in protocol amendment 5.

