## 5 Statistical methods: Analysis sets

For all analysis sets, subjects will be analyzed according to the study treatment(s) received. Subjects with dose reduction due to ALT/AST will be analyzed according to the treatment they received up to the dose reduction in Part 2.

The safety analysis set will include all subjects that received any study drug and experienced no protocol deviations with relevant impact on safety data.

The PK analysis set will include all subjects with at least one available valid (i.e., not flagged for exclusion) PK concentration measurement, who received any study drug and experienced no protocol deviations with relevant impact on PK data.

The PD analysis set will include all subjects with available PD data and no protocol deviations with relevant impact on PD data.

The analysis sets and protocol deviation codes are related as follows:

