### **7.2.3 Statistical model, assumptions and hypotheses**

The difference between each LJN452 dose and placebo will be assessed by Wilcoxon rank sum test for change from baseline in total PBC score and itch subdomain subscore at each visit. A two-sided p-value and 90% CI for each treatment difference will be reported with no adjustment for multiplicity. In addition, summary statistics (mean, median, SD, minimum, maximum) will be reported at each applicable time point.

As an additional secondary end point, a 100mm visual analogue scale (VAS) will be used to assess the severity of patients' itch as well as loss of sleep. The score (distance from left) on the VAS will be recorded for both parameters by the patient marking with a line. The distance marked will be converted to a score between 0 and 10.

The change from baseline in VAS scores for itch and sleep loss will be analyzed by repeated measures analysis of covariance. The model will include treatment as a fixed effect, time as a repeated effect, the treatment by time interaction, the visit by baseline interaction and baseline as a continuous covariate. An unstructured covariance matrix will be used. Two-sided 90% confidence intervals for the difference between each LJN452 dose and placebo will be presented for each visit. The UDCA and pruritus stratification factor will also be included as a fixed effect in the model for the Part 2 analysis. Missing values will not be imputed.

ALP data will be analyzed using the same approach as described in Section 7.1.3.

Additionally, the number and percentage of subjects who have  $ALP < 1.67 \times ULN$  with  $> 15\%$  reduction from baseline and a normal total bilirubin level will be tabulated by part, treatment and visit.

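### SAP 7.1.3 sets data after a dose reduction to missing without limiting this to the additional ANCOVA, so as written the protocol's all-data Part 2 primary analysis is lost

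*SAP*

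**What the plan says.** SAP 7.1.3 specifies a repeated measures ANCOVA of log GGT change, with Day 85 as the primary time point for Part 2. Its last paragraph notes that doses may be reduced in Part 2 and then says: "If for any subject the dose is reduced during the study, any data after the dose reduction will be set to missing". The sentence that follows is: "A repeated measures ANCOVA treating all measurements obtained post dose reduction as missing will be performed as well for Part 2 only". SAP 7.2.3 extends the approach to the secondary endpoint: "ALP data will be analyzed using the same approach as described in Section 7.1.3".

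Protocol 11.4.2 gives the same primary model and has no general missing rule. It only adds: "Additionally a repeated measures ANCOVA treating all post dose reduction measurements as missing will be performed as well". The data analysis row of the protocol synopsis says that the Part 1 model takes in every GGT value available over time, and that Part 2 uses that model with the stratification factor added. Protocol 11.5.1 refers ALP to 11.4.2.

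SAP 5 and protocol 11.1 share one further sentence: "Subjects with dose reduction due to ALT/AST will be analyzed according to the treatment they received up to the dose reduction in Part 2".

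Under protocol 6.2.1, once an ALT or AST rise is confirmed, "the study treatment will be reduced to the next dose level in a blinded manner". Table 6-1 moves Dose Level 2 to Dose Level 1, Dose Level 1 to placebo, and placebo to placebo. Placebo patients can therefore have sham reductions.

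**The concern.** The SAP sentence covers any subject and any data, and it is not tied to one model. If a programmer applies it to the analysis data set, the primary model never sees a post-reduction value. The additional ANCOVA then repeats the primary, and the analysis that the protocol calls primary is not run.

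The two analyses answer different questions at Day 85. With all data kept, the estimate is the effect of starting on a dose with reductions allowed. With post-reduction data removed under missing at random (SAP 7.1.4), it is the effect had nobody been reduced. Reductions follow liver enzyme rises, so they are tied to tolerability, and the step down differs by arm. The Part 2 primary objective is dose-response on GGT, so the choice can act unequally on the two doses being compared.

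**Working it through.** **1. The texts side by side.**

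| | Primary, Part 2 | Additional, Part 2 |
|---|---|---|
| Protocol (synopsis, 11.4.2) | all available values | post-reduction values missing |
| SAP 7.1.3 as written | post-reduction values missing | post-reduction values missing |

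The model terms are the same in both columns, so the SAP row gives one analysis twice. One simulated data set (50 patients, 6 of 30 active patients reduced, half the log effect lost) shows this. The protocol's primary gives a ratio of 0.495 (n = 50) and its additional analysis 0.458 (n = 44). Both SAP analyses as written give 0.458 (n = 44).

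**2. Does another sentence settle it?** The shared sentence in SAP 5 and protocol 11.1 can be an arm label or a data cut-off, so it does not. Module 8, which "contains programming specifications e.g. for derived variables and derived datasets", might, but it is not among the documents, and SAP 1.1 assigns the methodology to Module 3.

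**3. Inputs for an illustration.** From protocol 11.6 and 11.7: 30 versus 20 patients, GGT effect 50% with SD 0.28 (taken here on the log scale), ALP difference 15 points with SD 17.8, two-sided 5%. Assumed: a fraction f = 0.1, 0.2 or 0.3 of an arm reduced after Week 5. The share L of the effect lost is assumed to be 0.25 to 0.5 for Dose Level 2 (still on active drug) and 0.5 to 1 for Dose Level 1 (moved to placebo).

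**4. The plan's own figure.** The ALP standard error is 17.8 × √(1/30 + 1/20) = 5.14, and 15/5.14 = 2.92. Power from the noncentral t with 48 df is 81.6%, against 81% stated.

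**5. GGT with all data kept.** Ratio = 0.5^(1 − fL):

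| L | f = 0.1 | f = 0.2 | f = 0.3 |
|---|---|---|---|
| 0.25 | 0.509 | 0.518 | 0.527 |
| 0.5 | 0.518 | 0.536 | 0.555 |
| 1.0 | 0.536 | 0.574 | 0.616 |

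With post-reduction data missing at random, the ratio stays at 0.50. The 90% interval around 0.50 is 0.5 × exp(±1.677 × 0.0808), that is 0.437 to 0.573.

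**6. ALP power with all data kept.** The difference becomes 15 × (1 − fL):

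| L | f = 0.1 | f = 0.2 | f = 0.3 |
|---|---|---|---|
| 0.25 | 79.6% | 77.6% | 75.4% |
| 0.5 | 77.6% | 73.1% | 68.1% |
| 1.0 | 73.1% | 62.9% | 51.7% |

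**7. ALP power with post-reduction data missing, equal rates in placebo.** The planned repeated measures model borrows from earlier visits. With an assumed correlation of 0.6 and two earlier visits, R² = 2 × 0.36/1.6 = 0.45. The standard error grows by √(0.45 + 0.55/(1 − f)) = 1.03, 1.07, 1.11, and power is 79, 76 and 73%. Simulated inflation of 1.04, 1.08 and 1.12 gives slightly less. The range is about 78–79, 75–77 and 72–73%. A complete-case t-test (27 v 18, 24 v 16, 21 v 14) would give 77, 72 and 66%, but that is not the planned model.

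**The case against.** The strongest defence is context. The closing paragraph of SAP 7.1.3 reads naturally as one unit: reductions can occur, such data are set to missing, and an ANCOVA on that basis is run as well. Those last words would be pointless if the primary were already that analysis. SAP 1.2 lists the changes in this version, including the time-by-baseline term. On design it says only "The changes to the study design in protocol amendment 5", with no new handling of reductions. All of this stands. A reader might infer that the sponsor meant to replace the primary analysis. The documents do not support that, and loose drafting is the likelier explanation.

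A reader might also infer that the protocol itself leaves its primary open, since no sentence says outright that post-reduction values are kept. The synopsis and 11.4.2 together answer this: all available measurements go into the primary, and exclusion appears only as an addition. That makes the departure in the SAP clearer.

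It is also fair to say that the number of affected Day 85 values may be small. A persistent or new confirmed rise on the reduced dose leads to discontinuation, after which the minimum data collected are concomitant treatments and adverse events, although follow-up assessments are requested where possible. The study is also exploratory, with no multiplicity adjustment, and GGT power stays above 99.9% if up to 30% of one active arm loses its Day 85 values. These points limit the likely size, but none of them supplies the missing restriction in the SAP.

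**Conclusion.** The point holds as a mismatch between the SAP as written and the protocol, and it should be fixed. An unrestricted rule in SAP 7.1.3 removes the protocol's all-data primary analysis of GGT at Day 85. By cross-reference it does the same for ALP.

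The size is illustrative, because reduction rate, timing and loss of effect are all assumed. With 10 to 30% reduced, the two analyses would differ by about 0.01 to 0.05 on the GGT ratio for Dose Level 2 and 0.02 to 0.12 for Dose Level 1. Only the extreme Dose Level 1 cases reach or pass the upper 90% limit of 0.57. It would be wrong to conclude that one choice clearly protects ALP power. Keeping all data lowers power through a smaller effect, and dropping data lowers it through fewer values. The 66% figure should not be read as the power of the planned model, for which about 72 to 73% applies at 30% reduced.

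**What to change.** Before Part 2 unblinding, amend SAP 7.1.3, and 7.2.3 by reference, to say:

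> The primary Part 2 GGT model and the ALP model use all available measurements regardless of dose reduction, with subjects grouped by the treatment received before the reduction. Setting post-reduction data to missing applies only to the additional repeated measures ANCOVA, by the same rule in all arms including placebo.

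Grouping by treatment received keeps the basis already used in SAP 5 and protocol 11.1. If the dose-reduction sentence there is clarified as an arm label, it should be clarified identically in both documents. Module 8 should be checked against the amended text.

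The cost is two sentences, with no new data, visits or patients. The downside is that, if effect is lost after reductions, the headline GGT effect will be slightly smaller and ALP power will fall below the planned 81% (73 to 80% with 10% reduced, under the assumptions above). The additional ANCOVA remains available to show the result without post-reduction data.
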